### 2.3.2. Part B: Cold urticaria Subjects

Objectives	Endpoints
Exploratory	
Pharmacodynamic measure of Cold Provocation Assess change in Cold Temperature Test values	Pharmacodynamic measure of Cold Provocation 
 
Change from placebo of Cold Temperature Test values at day 3
 

Pharmacodynamic measure of Allergen Challenge Assess measure of weal and flare size, in subjects with Cold urticaria after allergen challenge (Skin Prick test, positive control (histamine) and negative control (saline)).	Pharmacodynamic measure of Allergen Challenge 
 
Percent of inhibition on day 3 will be derived for:               
 
The longest weal diameter (measured by ruler).
 
Perpendicular weal length (measured by ruler).
 
Weal area calculated using weal diameter and length assuming ellipse area.
 
 
 
Weal Volume as measured by;               
 
Quantitative volumetric morphometry
 
 
 
Flare Erythema as measured by;               
 
Mexameter
 
 
 

Systemic measure of target pharmacology Determine CD69 expression in an ex vivo blood sample following CD69 stimulation	Systemic measure of target pharmacology 
 
Percent inhibition of CD69 expressing cells in blood samples stimulated with anti-IgM .
 

1. Measured using digital camera using PRIMOS 5.075D instrument software produced by GMF
2. Measures erythema and melanin index values using narrow band spectrophotometry
3. TEMPTest 4.0

[figure not shown]

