## 5.4. Treatment Assignment

Subjects will be assigned to treatment in accordance with the randomization schedule generated by Parexel, prior to the start of the study. Randomisation will occur within each cohort of study. Subjects will be randomised to 1:1 to receive bilateral treatment of GSK2646264 or placebo in Part A. For Parts B & C, subjects will be randomised 3:1 active:placebo respectively, to receive either GSK2646264 or placebo.

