### 6.1.3. Part B: Cold urticaria Subjects Time and Event table

Day:	Screening	-1	1	2	3	4	Day 6 to 15	Follow-up (Day 17-19)	Notes
Visit Window (relative to Day 1)	-28 to -7 days 								1. Screening can occur on any day between 28 days and 7 days prior to Day 1 dosing.
Admission to Unit		X							
Informed Consent	X								
Demographics	X								
Complete physical	X							X	
Body weight (kg)	X								
Height (cm) without shoes	X								
Brief physical		X							
Medical/medication/drug/alcohol history	X								
12-lead ECG	X 	X			X			X	2. Triplicate ECG at screening and CV risk factors
Vital signs 	X	X	X	X	X		X	X	3. Should be performed at the same time points as PK samples are taken
Urine drug/alcohol screen	X	X							
Pregnancy Test (women) 	X(S)		X(S/U)			X (S)	X(S)		4. Pregnancy test will be performed 3 times during screening, serum on day -28, day -7 to -4, and a serum or urine pregnancy test the day of the start of the study prior to dosing and a serum pregnancy test between day 10-12 (to coincide with a PK sample) and at the follow up visit.
HIV, Hep B and Hep C screen	X								
Clinical Laboratory Tests	X	X			X			X	

Day:	Screening	-1	1	2	3	4	Day 6 to 15	Follow-up (Day 17-19)	Notes
Allergen Challenge-SPT	X 		X 		X 	X 			5. SPT- Skin Prick Test measurements will be performed ~15-20mins post challenge 6. SPT using all 4 specified allergens 7. SPT will be performed at 6 hours post dose (see Section 6.4.1), and at 24 hours post last dose on day 3 8. SPT will be performed pre-dose on Day 1
TSH, free T4, T4, T3	X					X	X 	X	9. One sample between day 10-12 to coincide with PK sample
Cold Temp Test (Temp Test 4.0)	X		X 		X 	X 			10. Pre-dose 11. 6 hours post dose 12. 24 hours post last dose on Day 3
Randomisation		X							
Tolerability Assessment			←-----X  -----→						13. Tolerability assessment at pre – and ~6 hours post-dose
AE assessment			←-----X-----→				X		
Concomitant Medication		X	←-----X-----→				X		
Pharmacokinetic Blood Sample			X 	X 	X 	X 	X 	X	14. PK blood sample taken at pre dose, 1, 4, 8, 12hr post dose 15. One PK sample to be taken 24 hours post last dose on Day 3 16. One PK blood sample per day will be taken as follows: PK samples will be obtained on the following days (± 1 day): Day 6, 9, 12, & 15.

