##### **9.1.1. Precision Estimation**

This study is designed to estimate the effect of GSK2646264 relative to Placebo on comparison of interest. No formal hypothesis will be tested. Point estimates and corresponding 95% confidence intervals will be constructed.

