## 9.2. Sample Size Considerations & Statistical Analyses

There are no formal hypotheses to be tested. An estimation approach will be taken and 95% confidence intervals will be constructed to provide a range of plausible values for the comparisons of interest.

Approximately 42 subjects will be randomised in total, consisting of 18 subjects in Part A (9 subjects on first dose group and 9 subjects in second dose group), 12 subjects in Part B and 16 subjects in Part C of the study. The sample size is based on feasibility and not driven by any formal hypothesis testing.

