
 To assess the pharmacodynamic effect of GSK2646264 on weal and flare sizes and erythema, in cold urticaria subjects after allergen challenge (Skin Prick test, positive control (histamine) and negative control (Saline)). 	
 Percent inhibition on days 1, and 3 for the longest weal diameter (measured by ruler). Percent inhibition on days 1, and 3 for perpendicular weal length (measured by ruler). Percent inhibition on days 1, and 3 for weal area (calculated). Percent inhibition on days 1, and 3 for Weal volume (measured by quantitative volumetric morphometry¹) Percent inhibition on days 1, and 3 for Flare erythema (measured by Mexameter²).

 To assess the effect of GSK2646264 on Cold Temperature Test values 	
 Change in Cold Temperature Test⁴ values at day 1 and day 3
Part C: Chronic Spontaneous Urticaria Subjects	Part C: Chronic Spontaneous Urticaria Subjects

 To assess the effect of GSK2646264 on weal characterisation in CsU subjects within treated area only To assess the Quality of Life in CsU subjects. To assess the disease activity in CsU subjects. To investigate the relationships between (basophil histamine release) BHR test and weal characteristics 	
 Urticaria Activity Score, a composite score using key urticaria symptoms (number of weals, Itch/Pruritus), to derive change from baseline on Day 1 through to Day 7 Change from baseline in total Dermatology Life Quality Index (DLQI) score Change from baseline in Angioedema Activity Score (AAS) Relationship of positive BHR test with reduction in number or size of weals
1 All Healthy subjects and the Cold Urticaria subjects should be screened for reactivity to one of the allergens used in skin prick test. (grass pollen, Dermatophagoïdes pteronyssinus, birch pollen and cat dander) 2 Measured using digital camera using PRIMOS 5.075D instrument software produced by GMF 3 Measures erythema and melanin index values using narrow band spectrophotometry 4 TEMPTest 4.0 5 Calculated as ellipse or oval area	

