- Individual = Represents FL related to any displays of individual subject observed raw data.
- Weal area derived from weal longest diameter and perpendicular length; assuming elliptic shape.

Table 7 Overview of Planned Pharmacodynamic Analyses for Part B

[Endpoint / Parameter/ Display Type]	Untransformed														
	Absolute							Percent of Inhibition/Change ¹							
	Stats Analysis			Summary		Individual		Stats Analysis			Summary		Individual		
	T	F	L	T	F	F	L	T	F	L	T	F	F	L	
Allergen Challenge - Part B: Cold Urticaria Subjects															
Weal area (mm ²)				Y	Y			Y				Y	Y	Y	Y
Weal volume (mm ³)				Y	Y			Y				Y	Y	Y	Y
Weal longest diameter (mm)				Y	Y			Y				Y	Y	Y	Y
Weal perpendicular length (Height) (mm)				Y	Y			Y				Y	Y	Y	Y
Flare erythema ((mm ²)				Y	Y			Y				Y	Y	Y	Y
Cold Temperature Test				Y	Y			Y				Y	Y	Y	Y

NOTES :

- T = Table, F = Figure, L = Listing, Y = Yes display generated.
- Stats Analysis = Represents TFL related to any formal statistical analyses (i.e. modelling) conducted.
- Summary = Represents TFL related to any summaries (descriptive statistics) of the observed raw data.
- Individual = Represents FL related to any displays of individual subject observed raw data.
- Summary will be presented by dose strength, BSA and day (if applicable)

1. Change will be produced for Cold Tem Test endpoint

Table 8 Overview of Planned Pharmacodynamic Analyses for Part C

[Endpoint / Parameter/ Display Type]	Untransformed											
	Absolute						Change from Baseline					
	Stats Analysis			Summary		Individual	Stats Analysis			Summary		Individual
	T	F	L	T	F	F	L	T	F	L	T	F
Pharmacodynamic - Part C: Chronic Spontaneous Urticaria Subjects												
UAS7 score				Y			Y	Y			Y	Y
Angioedema Activity Score (AAS)				Y			Y	Y			Y	Y
UAS7 components (Number of weals, Extent of Itch)				Y			Y	Y			Y	Y

NOTES :

- T = Table, F = Figure, L = Listing, Y = Yes display generated.
- Stats Analysis = Represents TFL related to any formal statistical analyses (i.e. modelling) conducted.
- Summary = Represents TFL related to any summaries (descriptive statistics) of the observed raw data.
- Individual = Represents FL related to any displays of individual subject observed raw data.
- Summary will be presented by dose strength, BSA and day (if applicable)

9.1.2. Planned Pharmacodynamic Statistical Analyses**9.1.2.1. Part C: Chronic Spontaneous Urticaria Subjects**

Planned Statistical Analyses
Endpoint(s)

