11.10.10. Pharmacodynamic and Biomarker Tables

Pharmacodynamic and Biomarker: Tables					
No.	Population	IDSL / TST ID / Example Shell	Title	Programming Notes	Deliverable [Priority]
Pharmacodynamics					
5.1.	PD	Non-Standard_PDT 1	Allergen Challenge, Weal Area - Summary Statistics (Absolute and Percent of Inhibition)	Absolute and Percent of Inhibition Part A + B	IA[1],SAC [1]
5.2.	PD	Example Non-Standard_PDT 1 modified based on endpoint.	Allergen Challenge, Weal Volume – Summary Statistics (Absolute and Percent of Inhibition)	Absolute and Percent of Inhibition Part A + B	IA[1],SAC [1]
5.3.	PD	Example Non-Standard_PDT 1 modified based on endpoint.	Allergen Challenge, Longest Weal Diameter- Summary Statistics (Absolute and Percent of Inhibition)	Absolute and Percent of Inhibition Part A + B	IA[1],SAC [1]
5.4.	PD	Example Non-Standard_PDT 1 modified based on endpoint.	Allergen Challenge, Weal perpendicular length - Summary Statistics (Absolute and Percent of Inhibition)	Absolute and Percent of Inhibition Part A + B	IA[1],SAC [1]
5.5.	PD	Example Non-Standard_PDT 1 modified based on endpoint.	Allergen Challenge, Flare Erythema - Summary Statistics (Absolute and Percent of Inhibition)	Absolute and Percent of Inhibition Part A + B	IA[1],SAC [1]

Pharmacodynamic and Biomarker: Tables					
No.	Population	IDSL / TST ID / Example Shell	Title	Programming Notes	Deliverable [Priority]
5.6.	PD	Example Non-Standard_PDT 1 modified based on endpoint.	Cold Temp Test, Change in critical temperature thresholds	Absolute Part B only	SAC [1]
5.7.	PD	Example Non-Standard_PDT 1 modified based on endpoint.	UAS7 Scores – Summary Statistics (Absolute and Change from Baseline)	Absolute and Change from Baseline Part C only	SAC [1]
5.8.	PD	Example Non-Standard_PDT 2	Change from baseline in composite total UAS7 Scores – Treatment Comparison	Paired t-Test (95%CI) and ANCOVA to compare treatments groups. Pre-Dose Value as Covariate Part C only	SAC [1]
5.9.	PD	Example Non-Standard_PDT 1 modified based on endpoint.	UAS7 Components – Summary Statistics (Absolute and Change from Baseline)	Absolute and Change from Baseline Part C only	SAC [1]
5.10.	PD	Example Non-Standard_PDT 2 modified based on endpoint.	Change from baseline in composite total UAS7 Components – Treatment Comparison	Paired t-Test (95%CI) and ANCOVA to compare treatments groups. Pre-Dose Value as Covariate Part C only	SAC [1]

Pharmacodynamic and Biomarker: Tables					

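### The SAP's Part B cold-test analysis still fits the superseded bilateral design, so under the 3:1 parallel design no listed output gives the difference from placebo that the protocol's Day 3 endpoint asks for

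*SAP*

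**What the plan says.** **Protocol (current)**

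- Section 2.3.2 gives the exploratory cold-provocation endpoint as "Change from placebo of Cold Temperature Test" values at Day 3. Section 9.1.1 says that the study estimates the effect relative to placebo: "Point estimates and corresponding 95% confidence intervals will be constructed".
- Section 5.4: "For Parts B & C, subjects will be randomised 3:1 active:placebo respectively". Section 9.2 plans "12 subjects in Part B and 16 subjects in Part C of the study".
- Section 6.1.3 schedules the cold test at screening, on Day 1 before dosing, on Day 3 at 6 h after dosing, and on Day 4 at 24 h after the last dose.
- Section 3.1.4 treats the first 4 patients on 10% BSA (Table 4) and the remaining 8 on 3.5% BSA (Table 5).
- Section 9.3.2.3.1 plans descriptive PD summaries for Parts A and B by strength, BSA and day. The cold test is not among the parameters that it names.

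**SAP**

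- The synopsis bases the SAP on amendment 2. Section 2.3 describes bilateral treatment of each subject. Section 2.1 declares endpoint changes for Part A only.
- Section 2.2 gives the Part B cold-test endpoint as change in "values at day 1 and day 3".
- Table 7 shows summaries and individual displays for the cold test, with the note "Change will be produced for Cold Tem Test endpoint". Its statistical-analysis columns appear empty.
- Table 5.6, "Cold Temp Test, Change in critical temperature thresholds", uses shell PD_T1 and carries a note asking for absolute values. Figures 5.11 and 5.12 show individuals, and means with 95% CIs, by treatment and day.
- Appendix 3 (Section 11.3.2.1) gives the cold test no baseline. Listing 32 asks for change from baseline.
- Appendix 8 mentions an ANOVA against placebo for PD parameters in general. The synopsis mentions paired t-tests and/or ANCOVA where applicable.

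**The concern.** The endpoint is a comparison with placebo. In a bilateral study that comparison lies within each patient: active side against placebo side, with no baseline needed. The SAP's layout suits that study. Amendment 3 replaced it with separate arms, so a patient no longer has a placebo value of their own, and the SAP defines no baseline to take its place. The word change then has no clear meaning. The SAP's Day 1 value is also, on the current schedule, a pre-dose reading that cannot show a drug effect.

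Protocol Section 3.2.1.2 names threshold testing, alongside allergen challenge, as the way to show target engagement in cold urticaria. If the outputs are produced as listed, the reader gets two arm summaries, one of them from three patients, and must form the contrast unaided. The alternative is to choose an analysis after the data are seen, by a sponsor who is unblinded.

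**Working it through.** **1. The plan's own precision figures.** Protocol Section 9.2.1 gives half-widths for Part A with n = 9. The formula t(0.975, 8) × SD / √9 gives 2.306 × 24 / 3 = 18.45 (stated 18.5), 2.306 × 11 / 3 = 8.46 (8.5) and 2.306 × 23 / 3 = 17.68 (17.7). They reproduce as t intervals. No precision figure is given for Part B, so the same approach is used below.

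**2. Inputs.** Twelve patients at 3:1 are 9 active and 3 placebo. The first four are 3 and 1. The remaining eight are 6 and 2 if the ratio is kept. The documents give neither the SD of the threshold nor the correlation ρ between Day 1 and Day 3, so results are in SD units over a range of assumed ρ.

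**3. Arm means, as the listed displays would show them.** Placebo: t(2) / √3 = 4.303 / 1.732 = 2.48 SD. Active: t(8) / √9 = 0.77 SD. These are intervals for single means and are not directly comparable with the interval for a difference.

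**4. Active minus placebo, unadjusted.** t(10) × √(1/9 + 1/3) = 2.228 × 0.667 = 1.49 SD. The average over simulated trials is 1.45, because the sample SD averages slightly below the true SD.

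**5. With the Day 1 threshold as covariate.** t(9) × 0.667 × √(1 − ρ²) = 1.508 × √(1 − ρ²), before any chance imbalance at baseline. Simulation of 9 v 3 (normal data) includes that imbalance:

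| assumed ρ | formula | simulated ANCOVA | simulated unadjusted |
|---|---|---|---|
| 0 | 1.51 | 1.55 | 1.45 |
| 0.3 | 1.44 | 1.48 | 1.45 |
| 0.5 | 1.31 | 1.34 | 1.45 |
| 0.7 | 1.08 | 1.11 | 1.45 |

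The two simulated widths are equal where 1.55 × √(1 − ρ²) = 1.45, that is at ρ ≈ 0.35. At ρ = 0.5 ANCOVA is narrower on average but wider in about 39% of simulated trials.

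**6. By treated area.** 3 v 1: t(2) × √(1/3 + 1) = 4.303 × 1.155 = 4.97 SD, with the spread estimated from the three active patients alone. 6 v 2: t(6) × √(1/6 + 1/2) = 2.447 × 0.816 = 2.00 SD. Estimates for each area on its own are therefore barely usable.

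**7. In degrees, for scale only.** If the SD were 2, 4 or 6 °C, the unadjusted half-width would be about 3.0, 5.9 or 8.9 °C. By the formula at ρ = 0.7 it would be about 2.2, 4.3 or 6.5 °C.

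**8. Does any listed output give the difference?** Shell PD_T1, used for Table 5.6, has treatment rows and no difference column. Shell PD_T2 has a column for the mean difference from placebo with its 95% CI, and Part C Tables 5.8, 5.10 and 5.12 use it. No cold-test display does.

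**The case against.** The best defence is that the SAP was coherent for the design it was written for. Shell PD_F1 says that each subject has one value for treatment and one for placebo. Table 7 puts the cold test's change in the same columns as percent inhibition, which Appendix 3 defines as control against treatment. With no baseline, change then reads naturally as within-patient change from placebo, and Figure 5.12 could show it with a CI. This stands as an explanation. It does not rescue the analysis, because a parallel design has no within-patient placebo value, and Listing 32 already conflicts with that reading.

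A reader might also infer more than the documents support:

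- **That no placebo comparison is planned at all.** Protocol Section 9.1.1, the SAP synopsis and Appendix 8 all promise one in general terms. What is missing is the link to a Part B model, table or shell.
- **That the 24 h test goes unused.** It is in both schedules, and the by-day displays and the listing can show it. It is not a named endpoint, and the Day 3 endpoint can be answered without it.
- **That the endpoint cannot be answered.** Arm means allow a crude difference. What is lacking is a pre-specified estimate with its interval.

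Two further objections stand. The endpoint is exploratory, in a first-in-human study without hypothesis tests. Baseline adjustment is also no certain gain with 12 patients. Pooling the two treated areas needs defending too, because the protocol asks for PD summaries by BSA.

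**Conclusion.** The point holds as a mismatch between the supplied SAP and the current Part B design. On the 3:1 parallel layout the SAP leaves change undefined, names a Day 1 value that is now pre-dose, and lists no output with the active-minus-placebo difference at Day 3. It is worth correcting, but it does not threaten the trial's primary safety objective.

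The achievable precision is modest either way: about 1.5 SD unadjusted, and about 1.3 or 1.1 SD with ANCOVA if ρ is 0.5 or 0.7. There is no gain at about 0.3 or below (about 1.48 against 1.45 SD). These figures assume 9 and 3 evaluable patients, roughly normal thresholds with equal spread in the two arms, and pooling over treated area. The values of ρ are assumptions. The conclusion about the outputs does not depend on them.

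It also rests on the one SAP supplied. The documents do not show whether a later SAP for Part B exists, so they do not support inferring that the sponsor never had a valid plan.

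**What to change.** - **SAP Section 2.2:** restore the endpoint as the active-minus-placebo difference in critical temperature threshold at Day 3 (6 h). Remove Day 1 as a response time point.
- **SAP Appendix 3:** define the Day 1 pre-dose threshold as the cold-test baseline, and reconcile this with Listing 32 and with the absolute-only note on Table 5.6.
- **SAP Table 7 and Section 11.10.10:** add a Part B cold-test table on shell PD_T2. Report the difference with its 95% CI from an ANCOVA of the Day 3 threshold on treatment, with the Day 1 pre-dose threshold as covariate. Present it as estimation only, which respects the no-testing policy. Add the Day 4 (24 h) test as a supportive time point.
- **Pooling:** state that the main estimate pools the 10% and 3.5% BSA patients, and show descriptive results by BSA. Both groups receive the same amount per unit area (9 g / 900 cm² = 6.3 g / 630 cm² = 10 mg/cm²), which supports pooling for a local skin test on treated skin.
- **Precision:** state the expected half-widths, so that a wide interval is not read as absence of effect.

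The cost is SAP wording and one table on an existing shell, with no new data. The statistical downside is one degree of freedom and a slightly wider interval if the baseline correlation is low.

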### 2.3.3. Part C: Chronic Spontaneous Urticaria Subjects

Objectives	Endpoints
Exploratory	
Pharmacodynamics as assessed by the Urticaria activity score  Urticaria Activity Score: Assess measures of weal characterisation in CsU subjects within treated area only	Pharmacodynamics as assessed by the Urticaria activity score 
 
Urticaria Activity Score, a composite score using key urticaria symptoms (number of weal, itch/pruritus), to derive change from baseline for the 7 days after dosing
 

To measure of Quality of Life	
 
Dermatology Life Quality Index (DLQI) questionnaire
 

To measure disease activity	
 
Angioedema Activity Score (AAS)
 

Investigate relationships between (basophil histamine release) BHR test and weal characteristics	
 
Relationship of positive BHR test with reduction in number or size of weals
 

Systemic measure of target pharmacology  Determine CD69 expression in an ex vivo blood sample following CD69 stimulation	Systemic measure of target pharmacology 
 
Percent inhibition of CD69 expressing cells in blood samples stimulated with anti-IgM.
 

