**Figure 3 Schematic showing Part B Dosing in Cold urticaria patients**

**3.1.5. Part C : A double-blind (sponsor unblinded) placebo-controlled, randomised to active or placebo treatment repeat dose study (3 doses over 7 days), in subjects with mild to moderate Chronic Spontaneous Urticaria (CsU)**

Subjects will be randomised to a 3:1 ratio to receive active treatment or placebo applied to areas of the body chosen by the investigator once a day every 3 days, over a total period of 7 days. Dosing will occur on days 1, 4 and 7. The chosen area where cream is applied will remain the same throughout the dosing period. Dosing in Part C will only commence once relevant data from the first four subjects in Part B have been reviewed, to allow greater confidence in predictions of the pharmacokinetics in Part C. The BSA over which study treatment will be administered in Part C will be 10%, but is subject to change, if appropriate, based on preliminary data from the first 4 subjects in Part C. However, the maximum BSA will not exceed 20% (see [Figure 4](#) for a visual representation of the dosing schedule).

[figure not shown]
The first 4 subjects of Part C will be randomised so that one of the 4 subjects will receive placebo and the three other subjects will receive GSK2646264. An informal review of the preliminary data from the first 4 subjects may be conducted after they have completed the study. PK, safety, and tolerability, up to and including the follow-up visit, will be reviewed by the Sponsor (See [Section 5.5](#)). If required, a discussion with the SMC regarding any changes or adjustments to the dosing regimen in Part C will be held. Recruitment of the full planned cohort (n=16) may continue during any data review.

The timing and the assessments to be completed at each visit are provided in the Time and Event tables ([Section 6.1.4](#)). Early termination of this patient group may occur due to feasibility of recruitment and stopping criteria see ([Section 5.5](#) and [Section 5.6](#)). Following inclusion in the study, subjects will be randomised. 10 mg/cm^2 of 1%

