#### **6.5.2. Part C**

##### **6.5.2.1. Urticaria Activity Score (UAS7)**

For the chronic spontaneous urticaria subjects in Part C, Urticaria activity score (UAS7), a composite endpoint, will be derived using key urticaria symptoms (number of weal, itch/pruritus):

UAS7 components will be captured using a daily diary for 7 days. The daily UAS7 score will be the sum of each key component score. A detail of UAS7 daily diary is provided in [Appendix 3](#). The days on which to record in the UAS7 diary are captured in the T&E Table (Section [6.1.4](#)). On days where dosing occurs, the UAS7 diary will be completed pre-dose.

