##### **6.5.2.2. The Angioedema Activity Score (AAS)**

For the chronic spontaneous urticaria subjects in Part C, the Angioedema Activity Score (AAS) will be captured during Screening, and between Day 2 and Day 8. Details of the questionnaire are provided in [Appendix 7](#). The days on which to record the AAS are

captured in the T&E Table (Section 6.1.4). On days where dosing occurs, the AAS will be completed pre-dose.

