### URTICARIA ACTIVITY SCORE - 7 (UAS-7) DIARY

1. Wheals  yes →  no ↓	
 
 
How many wheals/ erythemas have appeared during the last 24 hours?
 
 <20    <1 cm    <1 cm    <3 hrs    <3 hrs
 
 20-50    1-5 cm    1-5 cm    3-12 hrs    3-24 hrs
 
 >50    >5 cm    >5 cm    >12 hrs    >24 hrs
 
 
 
What average size did these wheals/ erythemas have during the last 24 hours?
 
 <20    <1 cm    <1 cm    <3 hrs    <3 hrs
 
 20-50    1-5 cm    1-5 cm    3-12 hrs    3-24 hrs
 
 >50    >5 cm    >5 cm    >12 hrs    >24 hrs
 
 

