2.3. Study Design

Overview of Study Design and Key Features	
Part A Healthy Volunteers 1 ^o :Safety +Tolerability 2 ^o : PK (0.2%-20% BSA) Exploratory: PD: Skin Prick Test: - Weal and flare (D1, D3, D7) Duration of response effect (D7) Each strength N=9	Part B Cold Urticaria Patients (N=12) 1 ^o : Safety +Tolerability 2 ^o : PK (~5% BSA) Exploratory: PD: SPT Weal and flare (D1, D3) Cold temperature test (D1, D3) Maximum tolerated strength
Key: PD – Pharmacodynamics PK – Pharmacokinetics BSA – Body Surface area SPT – Skin prick test 1 ^o - Primary objective 2 ^o - Secondary Objective	Part C Chronic Spontaneous Urticaria (N=12) 1 ^o : Safety +Tolerability 2 ^o : PK (~ 20% BSA) Exploratory: PD (weal, flare, itch D1-D7) Quality of Life Maximum tolerated strength
Design Features	
 This is a randomized double blind (sponsor unblinded), single, bilateral and repeat ascending dose First Time in Human study designed to evaluate the safety, tolerability, pharmacokinetics and pharmacodynamics of GSK2646264 or matching placebo conducted in three parts: Part A (healthy subject cohort, inpatient), Part B (cold urticaria subject cohort, inpatient) and Part C (chronic spontaneous urticarial subject cohort, outpatient).
Dosing	
 There will be a 7-28 day period from screening to admission to the clinic on Day -1. Subjects randomised on Day -1 in Part A and B and on Day 1 in Part C of study. Dosing will start on Day 1. The cream will be applied at 10 mg/cm² for all doses but the dose escalation is based on both increase in cream strength (0.5 % strength for Group 1 Part A; and if data permits 1.0% strength for Group 2 Part A), and increase in surface area of the body on which the cream will be applied. The escalation based on body surface area (BSA) starts at 0.2% BSA, then 1%, then 5% BSA, then 10% BSA,. For the study, the total BSA has been chosen as 1.8 m² and will not be measured individually, so the surface area on which the cream is applied is similar for all subjects as follows, regardless of their weight and height. All weights of cream are nominal and any one dose will not exceed 40 g.

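### The SAP keeps a Day 1 to 7 window for UAS7, while the current protocol points to Days 2 to 8; as written, the SAP leaves out the only diary entry made after the third dose.

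*SAP*

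**What the plan says.** **SAP.** Section 2.2 derives the Part C UAS7 endpoint "to derive change from baseline on Day 1 through to Day 7". The design overview in 2.3, Table 11 in Appendix 3 and the Part C schedule in Appendix 2 (11.2.1.4) use the same seven days. That schedule also puts AAS on Days 1 to 7 and the post-dose DLQI on Day 7. Section 9.1.2.1 sums seven consecutive days without numbering them. The synopsis says that the SAP follows protocol Amendment 2, and section 2.1 declares no departure on the UAS7 window.

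**Current protocol (Amendment 5).** Section 2.3.3 uses the composite score "to derive change from baseline for the 7 days after dosing". On dosing, section 3.1.5 says "Dosing will occur on days 1, 4 and 7". On completion, section 6.5.2.1 says "On days where dosing occurs, the UAS7 diary will be completed pre-dose". The form in Appendix 3 asks about weals that "have appeared during the last 24 hours", and its itch questions use the same recall. For AAS, section 6.5.2.2 says that it "will be captured during Screening, and between Day 2 and Day 8". Section 6.6.1 puts the post-dose DLQI on Day 8. In the Time and Events table (6.1.4), the UAS7 row is laid out like the AAS row: a screening entry, an empty cell under Day 1, then entries through Day 8. Section 9.3.2.3.2 subtracts the screening total from the post-dose total and leaves further detail to the RAP.

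**The concern.** The two documents give different seven-day windows for the same score. They share Days 2 to 7 and differ at the ends: the SAP has Day 1, the protocol has Day 8. Both ends matter. An entry made before the first dose, looking back 24 hours, describes untreated time only. An entry made on Day 7 before that day's dose cannot reflect the third application, so Day 8 is the only diary day that can.

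What is at stake is the Part C treatment comparison on UAS7, and on AAS if the SAP schedule is followed. The protocol plans these as ANCOVA estimates with 95% intervals, in about 16 subjects randomised 3:1. A program written to the SAP window would ignore scheduled data from the period of greatest cumulative dosing. It would also have to fill, or wrongly use, a Day 1 slot.

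**Working it through.** Neither document gives a figure for this point, so the check is a day count followed by an illustration.

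**Inputs.** Doses on Days 1, 4 and 7 (Protocol 3.1.5); entry before the dose on dosing days (6.5.2.1); 24-hour recall (Appendix 3); SAP window Days 1 to 7 (SAP 2.2); protocol window Days 2 to 8 (2.3.3, with the table in 6.1.4 and the AAS wording in 6.5.2.2).

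**Doses given before each entry.** For an entry on day d, count the dosing days earlier than d:

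| Entry day | 1 | 2 | 3 | 4 | 5 | 6 | 7 | 8 |
|---|---|---|---|---|---|---|---|---|
| Doses before entry | 0 | 1 | 1 | 1 | 2 | 2 | 2 | 3 |

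**Entries after 0, 1, 2 and 3 doses.**
- SAP, Days 1 to 7: 1, 3, 3, 0.
- Protocol, Days 2 to 8: 0, 3, 3, 1.

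Both windows have seven slots and share six.

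**What happens to the Day 1 slot.** If no Day 1 entry exists, as now scheduled, the missing-day rule in SAP Appendix 5 applies. Six scores meet the minimum of four, and their sum is multiplied by 7/6. If a Day 1 entry is made and counted, it adds an untreated day.

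**Size, under two assumed effect shapes.** Neither shape is in the documents.

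Constant effect e on each day after the first dose:
- Days 2 to 8: 7e.
- SAP window, Day 1 empty: 6e × 7/6 = 7e. Dilution 0%.
- SAP window, Day 1 counted: 6e. Kept 6/7 = 85.7%; dilution 14.3%.

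Effect proportional to doses received, one unit per dose:
- Days 2 to 8: 1+1+1+2+2+2+3 = 12.
- SAP window, Day 1 empty: (1+1+1+2+2+2) × 7/6 = 9 × 7/6 = 10.5. Kept 10.5/12 = 87.5%; dilution 12.5%.
- SAP window, Day 1 counted: 9. Kept 9/12 = 75%; dilution 25%.

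These figures are for UAS7. SAP Appendix 5 does not impute missing AAS values, so the 7/6 step would not apply to AAS, and the SAP does not say how an AAS total with an empty day is formed.

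**The case against.** **No pre-dose day need be counted.** A reader might infer that the SAP necessarily counts an untreated day and dilutes the effect by 14%. The documents do not support that. The current schedule has no Day 1 diary, so the likelier result is six prorated days, with no dilution under a constant effect. The 14% needs a Day 1 entry that is not scheduled. This stands, and the size must be given conditionally.

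**Days 2 to 8 is not stated in words for UAS7.** The explicit wording belongs to AAS; for UAS7 the days are read from a table row whose cells are imperfectly reproduced. The diary form labels its dosing-period entries Day 1 to Day 7, so the SAP's phrase could be read as those seven ordinal entries, in which case Day 8 is not lost. Part of this stands. However, the form labels its screening entries Day 1 to Day 7 as well, so the labels look like entry numbers. The SAP schedule places its marks under study days. The protocol's endpoint wording and its pre-dose rule fit Days 2 to 8. The ambiguity is itself a reason to state the mapping.

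**The SAP analysis sections do not impose the window.** Sections 9.1.2.1 and 9.1.2.2 give no day numbers. True, but then nothing corrects section 2.2 or the schedule. For DLQI the practical risk is small, since Day 8 is the only post-dose assessment the protocol schedules.

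**The weight is small.** UAS7 is exploratory and no hypothesis is tested. With 12 against 4 subjects and one covariate (16 − 3 = 13 degrees of freedom), the 95% half-width is about 2.16 × √(1/12 + 1/4) = 1.25 residual SD. Losing 14% of an assumed 1 SD effect is 0.14 SD, about one-ninth of that. This stands as a limit on importance.

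**It is one symptom of an outdated SAP.** Also true. But a general update could miss it, because the protocol's UAS7 text has no day numbers to copy.

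**Conclusion.** The mismatch is real and should be corrected. Applied as written to the current three-dose schedule, the SAP window omits Day 8, the only diary entry after the third dose, whether or not a Day 1 entry exists. Its Day 1 slot is either empty and prorated over, or holds an untreated day.

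The effect on the estimate depends on assumptions outside the documents: 0% or 14% dilution with a constant daily effect, and 12.5% or 25% with an effect proportional to doses received. The lower figure in each pair is for an empty Day 1. An unconditional statement that the treatment effect is biased toward zero would go too far. Reading the UAS7 window as Days 2 to 8 rests on the endpoint wording, the pre-dose rule, the table layout and the parallel AAS text together. No primary or secondary result and no sample size is affected.

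**What to change.** In SAP 2.2, 9.1.2.1 and 9.1.2.2, define the post-dose UAS7 and AAS totals as the sum of the entries on study Days 2 to 8, with the seven screening days as baseline. Carry the same days into SAP 2.3, Table 11 and the Part C schedule in Appendix 2, and use Day 8 for the post-dose DLQI. Add a rule that links the diary form's dosing-period labels 1 to 7 to study Days 2 to 8, using the date recorded on each entry.

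The cost is SAP wording and a derivation rule. The entries are already scheduled, so no new data collection is needed. It should be done before the Part C outputs are programmed, ideally as part of bringing the SAP up to the current protocol.
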